#### 11.2.4. Follow-up Visits 8 and 9 (Study Days 169 and 253)

At Visits 8 and 9 (Study Days 169 and 253), 12-Lead ECGs, physical examinations (abbreviated at Visit 8; full exam at Visit 9, with height/weight), vitals will be performed. Serum samples will be collected for PK and ADA analysis as detailed in Section 13.2. Blood will be collected for laboratory testing and viral serology, and urine collected for urinalysis. Urine pregnancy tests will be conducted for women of childbearing potential. Changes to concomitant medication will be assessed and recorded as well as AEs and SAEs. CSF will be collected at Visit 9 (Study Day 253).

In Study Visits 8 and 9, subjects will have all efficacy and QoL assessments performed (see the Schedule of Events for specifics, Table 6), in the following order:

- ISNCSCI
- GRASSP. Note: GRASSP prehension ability and prehension performance testing will be video recorded.
- Modified Ashworth Scale, fingers and thumb excluded
- SCIM III Self-Care & Mobility subscores
- Brief Pain Inventory
- Neuro-QOL Item Bank v1.0 Upper Extremity Function (Fine Motor, ADL)
- SF-36 v2 Health Survey
- CUE-Q
- PGIC Chronic SCI
- International Standards to document remaining Autonomic Function after Spinal Cord Injury (ISAFSCI)

GRASSP prehension ability and prehension performance testing will be video recorded.

# 12. INVESTIGATIONAL PRODUCT MATERIALS AND MANAGEMENT

Investigational product will be provided to the clinical sites.

## 12.1. Study Drug

Single-use vials with labels and an outer fiberboard carton with a single panel label will have the following information:

- LEI hNgR(310)-Fc Drug Product
- Concentration: 10 mg/mL
- Volume: 5 mL
- Storage:  $\leq$  65° C
- Caution: Filter Before Use New Drug-Limited by United States Law to Investigation Use Only
- Manufactured by

The clinical trial supply label will be in accordance with ICH GCP and local requirements for investigational product labelling.

# 12.2. Investigational Product Packaging and Labeling

Investigational products are for investigational use only and the products supplied for this study are intended for use only within the context of this study. The investigational product supplied for this study should be stored in a secure, temperature controlled, locked place with restricted access, maintained under adequate security until dispensed for subject use or returned to the sponsor.

For all shipments of study drug, site study personnel shall note a 6-month use limit date based on the date of thaw of the vials. A label will be supplied to record the thaw date and storage use limit date on the box containing the vials. Placebo expiry shall be defined in a memo included with the shipment and will be extended as warranted via memo when new stability data becomes available. A label will be supplied to record the expiry date on the box containing the vials. The label shall be updated if the expiry is extended before the placebo in the box is fully depleted.

# 12.3. Investigational Product Storage

AXER-204 is formulated as an isotonic solution in Phosphate Buffered Saline and is provided in 5 mL vials. It will be shipped to sites frozen at -80 °C (on dry ice). Upon receipt it shall be placed in the refrigerator at 2-8 °C in a secure location and allowed to thaw for a minimum of 16 hours prior to use in dose preparation. Once thawed, AXER-204 shall be kept stored in the refrigerator at 2-8 °C for up to 6 months prior to use. After thawing, the vials containing AXER-204 should NOT be shaken or vigorously agitated as this may result in generation of foam and particles. Contact the sponsor for instructions in the event there is a deviation from the required storage conditions.

Placebo consists of Phosphate Buffered Saline and is provided in 5 mL vials. It will be shipped to sites at a temperature of 2-8 °C. Upon receipt it shall be placed in the refrigerator at 2-8 °C.

# 12.4. Investigational Product Preparation

Refer to the dose preparation appendix in the Pharmacy Manual describing the details regarding dose preparation.

# 12.5. Investigational Product Management

The pharmacist or their designee will verify that investigational product supplies are received intact and in the correct amounts by signing and dating the investigational product receipt section at the bottom of the packing list. The person receiving the supplies must verify that the shipment contains all the items noted in the shipment inventory. Any damaged or unusable investigational product in a given shipment will be documented in the study files. The pharmacist must notify the sponsor or designee of any damaged or unusable investigational product supplied to the site.

The site will maintain a Study Drug and Placebo Inventory Log (includes, but not limited to, the following: lot number, number of units received, expiry date, and number of vials and syringes dispensed. The site will also maintain patient-specific investigational product dispensing logs.

An overall accountability of investigational product will be performed and verified throughout the study and at the site closeout visit. Upon completion of the study, copies of the investigational product accountability records will be returned to the sponsor. All used and unused study investigational product supplies will be inventoried and accounted, and any used or unused supplies which have not been destroyed locally shall be returned to the sponsor or designee at the end of the study. By signing the Investigator Agreement page of this protocol, the investigator agrees not to supply investigational product to any person(s) not enrolled in the study.

# 12.6. Investigational Product Accountability

Subjects will be treated at the clinical site, in-patient clinical unit, or other approved location and therefore the Pharmacist or other investigational staff via documentation of receipt of the investigational product and dosing/treatment given will perform/maintain accountability.

# 12.7. Investigational Product Handling and Disposal

Records of receipt, dispensing records and inventory forms, as applicable, will be examined and reconciled during and at the end of the study. Both the investigational product that is used during the study, as well as any remaining unused investigational product, must be accounted for on study drug and placebo accountability records provided to the PI by the sponsor or their designee or documented per site SOPs.

At the end of the study or when instructed by the sponsor or designee, all used and unused investigational product vials, accompanied by a packing slip, must be returned to the designated clinical supplies vendor for disposal or destroyed per site SOPs. If used investigational product vials and/or unused but expired investigational product vials were destroyed locally per site policies or procedures, destruction should be documented on the accountability log.

In addition, a copy of all completed investigational product accountability records must be retained in the Investigators' Study Files, with a copy sent to the sponsor or their designee. The product is to be stored in a safe place (locked facility) at the appropriate temperature.

## **13.** ASSESSMENT OF EFFICACY AND PHARMACOKINETICS

#### 13.1. Efficacy

Site personnel will be trained and certified to perform the efficacy assessments. The same raters will be used for evaluation of a given subject insofar as possible. Raters will be blinded to treatment for Part 2 of the trial.

#### 13.1.1. Part 1

Part 1 is focused on safety, tolerability, and pharmacokinetics. However, a subset of efficacy assessments are included, as follows:

- ISNCSCI. ISNCSCI is a comprehensive clinician-administered neurological exam for SCI. It is widely used for research and clinical (neurologic) description to fully assess sensory and motor functioning and level of injury in traumatic SCI. The UEMS will be calculated from the full ISNCSCI and evaluated separately.
- GRASSP [Kalsi-Ryan 2012a, Kalsi-Ryan 2012b]. GRASSP is a clinician administered test with three subset scores that assesses strength in 10 key muscles in the upper extremity as well as dexterity and fine motor skills.
- SCIM III self-care and mobility scores [Catz 2007, Itzkovich 2007]. SCIM III measures functional outcomes in three sections: self-care, respiration and sphincter management, and mobility. The current study will employ the self-care and mobility subscores.

#### 13.1.2. Part 2

The primary objective of Part 2 is to evaluate the safety, tolerability, and pharmacokinetics of repeat dosing. In addition, a number of efficacy assessments are included as secondary endpoints. The key secondary efficacy endpoint for Part 2 will be within-subject change from pre-treatment baseline and slope for UEMS as compared to placebo. The UEMS is collected as part of the ISNCSCI (Appendix 3).

Additional secondary efficacy endpoints will include changes from pre-treatment baseline and slope for:

- Graded Redefined Assessment of Strength, Sensation and Prehension (GRASSP) prehension performance scores. GRASSP is a clinician administered test with three subset scores that assesses strength in 10 key muscles in the upper extremity as well as dexterity and fine motor skills (Appendix 4).
- Version III of the Spinal Cord Independence Measure (SCIM III) self-care. SCIM III measures functional outcomes in three sections: self-care, respiration and sphincter management, and mobility. The current study will employ the self-care and mobility subscores. The evaluation will be administered by a clinician (Appendix 8).

Exploratory functional endpoints will include within-subject changes from pre-treatment baseline and slope for:

• ISNCSCI lower extremity motor and sensory scores

- GRASSP strength, sensation and prehension ability scores
- SCIM III mobility scores
- Patient Reported Outcomes
  - CUE-Questionnaire (CUE-Q) [Marino 2012, Marino 2015]. Assesses subject-reported upper limb function (Appendix 2).
  - SF-36 v2 Provides an investigator-evaluated Quality of Life (QoL) assessment for subjects. SF-36 will provide data on the subjects' perceived health and wellbeing over the course of the study (Appendix 6).
  - Neuro-QOL Item Bank v1.0 Upper Extremity Function (Fine Motor, ADL) -(Appendix 7).
  - PGIC Chronic SCI (Appendix 10) Provides a patient-reported global impression of change in the symptoms, activity limitations, emotions and overall quality of life with chronic spinal cord injury since beginning the trial.
- ISAFSCI [Krassioukov 2012]. The ISAFSCI will be used to document autonomic control of the heart, blood pressure, sweating and temperature regulation. Lower urinary tract function, bowel function, and sexual function will be scored (Appendix 1).

Exploratory biomarkers of target engagement and axonal growth may be assessed.

Since the mechanism of action entails enhanced axonal growth and plasticity, changes attained through Study Day 169 are anticipated to be most relevant to assessing on-target effects of therapy.

### **13.2. Pharmacokinetics**

Both serum and cerebrospinal fluid samples will be collected for analysis, as shown in Table 10 and Table 11.

In Part 1, a window relative to the nominal timepoint is allowed for sample collection as follows:

- Blood serum pharmacokinetic samples will be collected at 0 hour (immediately predose), and 1 h (±10 min), 6 h (±10 min), 12 h (±10 min), and 24 h (±10 min) postdose, as well as at Study Day 4 (72h ± 10 min), 8 (±1d), 15 (±3d), and 29 (±4d).
- Cerebrospinal fluid samples (CSF) will be collected via lumbar puncture at 0 hour (immediately pre-dose), 24 h (±2h) Study Day 4 (72 h ±4h), and Study Days 8 (±1d), and 29 (±4d).

The timing for serum and CSF sample collection may be adjusted for subsequent cohorts based on pharmacokinetic data from the preceding cohorts. Serum PK samples collected at pre-dose and on Study Days 8 and 29 will be analyzed for the presence of anti-drug antibodies (ADA).

In Part 2, Visits 3-7 (Study Days 21, 42, 63, 84, 104) will have a window of  $\pm 5$  days and Visits 8 and 9 (Study Days 169 and 253) will have a window of  $\pm 7$  days. CSF samples will be collected for PK analysis pre-dose on Study Days 1, 21, 42, 63, 84, and 104. The CSF sample collected on Study Day 253 will also be analyzed for PK. Serum samples will be collected for

PK analysis pre-dose and 4 h post-dose on Study Days 1, 21, 42, 63, 84, and 104. Serum will also be collected for PK analysis on Study Days 169 and 253. Pre-dose serum will be collected for ADA analysis on Study Days 1, 21, 42, 63, 84, and 104. Serum will also be collected for ADA analysis on Study Days 169 and 253. A subset of the CSF samples may also be analyzed for ADAs depending on development and presence of ADAs in the serum. Part 2 serum and CSF from subjects receiving placebo will be collected but will not be analyzed for PK and ADAs.

In Part 2 on Study Days 1, 21, 42, 63, 84, and 104 a window relative to the nominal timepoint is allowed for sample collection as follows:

- Serum pharmacokinetic samples will be collected at 0 hour (within 4 h pre-dose), and 4 h ( $\pm 10$  min) post-dose
- Cerebrospinal fluid samples (CSF) will be collected via lumbar puncture at 0 hour (immediately pre-dose)

	Day 1 (Dosing day)	Day 2 (24 hours post-	Day 4 (72 hours post-	Day	Day	Day	
		dose)	dose)	8	15	29	
Cerebrospinal Fluid	Pre-Dose	Х	Х	Х		Х	
Serum	Pre-Dose, and post-dose at Hours 1, 6,	Х	Х	Х	Х	Х	
	12						
Serum aliquot for ADA	X (Pre-dose)			Х		Х	
testing							

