# 7. INVESTIGATIONAL PLAN

### 7.1. Overall Study Design

Study RNX-AX204-101 is a two-part study that will be run sequentially, with Part 2 planned to start after Part 1 has completed. Each Part will be conducted at approximately 5 centers in the United States.

For each Part, eligible subjects will be ages 18 to 65 years inclusive, male or female, with a traumatic spinal cord injury that occurred at least 1 year prior to the screening date. Subjects must have significant neurological impairment of the hands and arms. Subjects who participated in Part 1 may be evaluated for enrollment in Part 2 provided at least 6 months will have elapsed between the dose received in Part 1 and the initiation of dosing in Part 2.

#### 7.1.1. Part 1

Part 1 is a multicenter, open-label, single ascending dose study in subjects with chronic spinal cord injury. Four cohorts of 6 subjects each are planned, with subjects within each cohort expected to receive the same dose of study drug. Thus, up to 24 subjects will be enrolled in Part 1, and all will receive AXER-204.

If the Maximum Tolerated Dose (MTD) is reached prior to the fourth cohort, the sponsor may enroll the remaining subjects (up to a total enrollment of 24 for the study) to obtain further data at the tolerated dose levels. The sponsor in conjunction with the investigators and medical monitor will determine dose escalation according to the methods described in Section 7.3.3.

Study drug will be administered sequentially, with at least 3 days between subjects being dosed within each cohort (following 72-hour safety assessment review by the sponsor in conjunction with the investigators and medical monitor for each prior subject).

The study stages for Part 1 are:

- Screening (within 84 days prior to Day 1). Patients have 84 days from the time of signing informed consent to complete their screening assessments and, if needed, their washout period for prohibited concomitant medications. The screening laboratory tests must be completed within 28 days prior to Day 1.
- Treatment period: Check-in Day 1, administration of study drug, 3-night in-clinic stay, and discharge on Day 4 following the completion of all scheduled procedures.

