At the initiation of the study, the study site will be instructed on the method for breaking the blind. A formal unblinding process will be used to ensure security and maintenance of the blind. However, the investigator should contact the sponsor before breaking the blind. When the blind has been broken for a subject, the reason must be fully documented and entered on the source document and eCRF for that subject.

Data that may potentially unblind the treatment assignment (eg, PK samples) will be handled such that the integrity of the blind is maintained and the potential for bias minimized. This may include making special provisions such as segregating the data in question from view by the investigator and site study staff, sponsor clinical team, and others as appropriate. The bioanalytical laboratory personnel will be open to the randomization codes in order to facilitate PK analytical work and ADA testing. Personnel are not to communicate or imply in any manner, information associated with this to others at the clinical site, the sponsor, its consultants, designated CRO, or other vendors.

A formal analysis of the data will be performed once all subjects have completed their treatment period and follow-up assessments through Day 169. This efficacy analysis will be performed as the primary assessment of efficacy in the study; the study will continue through the follow-up period to Study Day 253. A second efficacy analysis will be conducted at Study Day 253.

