3.2 Safety Variables

The following safety variables will be included for both Part 1 and Part 2:

- Study treatment exposure;
- Treatment-emergent adverse events (TEAEs);
- Clinical laboratory tests including hematology, clinical chemistry, and urinalysis;
- Physical examinations;
- Vital signs;
- 12-lead electrocardiograms (ECGs);
- Condition-specific safety outcomes, including the following:
 - Spasticity. Modified Ashworth Scale (MAS) (Pandyan et al. 1999) is a clinician administered examination for spasticity which measures muscle tone around selected limb joints. The total MAS score will be calculated and summarized for both part 1 and part 2. In addition, for part 2, bilateral total scores for Elbow, Wrist, Hamstrings, Quadriceps, Gastrocnemius, and Soleus will be analyzed to compare between treatment group with control group.
 - Pain. Brief Pain Inventory (BPI) (Cleeland and Ryan 1994) is a selfadministered questionnaire used to assess the severity of a subject's pain and the impact of this pain on the subject's daily functioning. The following scores will be calculated and summarized:
 - BPI pain severity for each of the four severity items ("worst," "least," "average," and "now"). For part 2, mean BPI pain score at Study Day 169 and change from baseline will be analyzed to compare treatment group with control group.
 - BPI pain interference. For part 2, mean BPI pain interference score at Study Day 169 and change from baseline will be analyzed to compare treatment group with control group.

4. Pharmacokinetic variables

- Serum and CSF samples will be collected and analyzed for concentrations of AXER-204 at planned time points following the schedules for Part 1 or Part 2, as described in the protocol.
- Pharmacokinetic (PK) parameters will also be determined (section 8.6.1) using a non-compartmental approach (NCA) for Part 1.

5. Immunogenicity variables

Pre-dose Anti-drug antibody (ADA) serum will be collected for ADA analysis for both Part 1 and Part 2 following the protocol defined schedule. The following immunogenicity variables will be analyzed:

• Anti-drug antibody (ADA) incidence

6. Analysis Population

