6.6 Antidrug Antibody Analysis Set (Part 1 and Part 2)

The Antidrug Antibody (ADA) Analysis Set will include all subjects who received at least 1 dose of study treatment and had at least one post-baseline ADA. This analysis set will be used to summarize ADA results. Subjects will be analyzed according to their randomized treatment.

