8.7 Immunogenicity Analysis

All anti-drug antibody (ADA) data collected in eCRF will be listed for the ADA analysis set. Positive ADA status for a sample is defined as having the screen assay reported as detected and the confirmatory assay reported as confirmed. Negative ADA status for a sample is defined as either having an assay reported as negative or having the screen assay reported as detected and the confirmatory assays reported as not confirmed.

The number and percentage of subjects with positive or negative ADA status will be summarized by dose cohort for Part 1 or by treatment group for Part 2 and time point.

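### SAP 8.7 defines Part 2 antibody positivity without reference to Day 1, and plans a by-treatment-group table whose placebo column must be empty

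*Protocol*

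**What the plan says.** On testing, Protocol 13.2 schedules Part 2 serum for ADA before dosing on Days 1, 21, 42, 63, 84 and 104, and again on Days 169 and 253. It then states: "Part 2 serum and CSF from subjects receiving placebo will be collected but will not be analyzed for PK and ADAs". The synopsis gives the same rule.

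On analysis, SAP section 5 names one immunogenicity variable, "Anti-drug antibody (ADA) incidence". SAP 8.7 defines it at sample level: "Positive ADA status for a sample is defined as having the screen assay reported as detected and the confirmatory assay reported as confirmed". For the summary it says that "ADA status will be summarized by dose cohort for Part 1 or by treatment group for Part 2 and time point". The ADA set in SAP 6.6 "will include all subjects who received at least 1 dose of study treatment and had at least one post-baseline ADA", with subjects placed in their randomised arm. It is not limited to AXER-204, and SAP 8.2 counts it by treatment group.

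On earlier exposure, Protocol 7.1 says "Subjects who participated in Part 1 may be evaluated for enrollment in Part 2", provided at least 6 months separate the Part 1 dose from the start of Part 2 dosing. Every Part 1 subject received AXER-204. Prior receipt in Part 1 is a randomisation stratum (Protocol 10.4.2), a term in the main efficacy model (SAP 8.5.2.1) and a planned efficacy subgroup (SAP 8.5.2.1.3). SAP 8.7 does not use it.

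**The concern.** An incidence should count new events. The SAP's rule counts positive samples, whatever the subject's status before the first Part 2 dose. In a trial that may re-enrol people already given the same protein, a count at a Part 2 visit can mix three things: antibodies present before any exposure, antibodies left from Part 1, and antibodies raised by repeat dosing. Only the third describes the Part 2 regimen.

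The second problem is a mismatch between the two documents. A programmer following SAP 8.7 would build a two-arm table, and a reader would expect a placebo comparison that the protocol rules out.

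At stake is how immunogenicity of a repeat-dose protein therapeutic is reported. Protocol 14.2.3 lists possible immune and allergic reactions first among its events of special interest, so the ADA table is likely to be read alongside them.

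**Working it through.** The documents give no ADA rate, assay cut-point or ADA sample size, so there is no planned figure to reproduce. The check sets passages side by side and adds a short illustration.

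**Placebo column.**
- Protocol 13.2 and synopsis: placebo samples are drawn but not assayed for ADA.
- SAP 8.7: a sample is positive or negative only through a reported assay result. An unassayed sample is neither.
- SAP 6.6: membership needs a post-baseline ADA. If that means a result, no placebo subject qualifies. If it means a sample drawn, placebo subjects enter the set with no status.
- SAP 9.3 records that an ADA set was added. It does not say that placebo samples will now be tested.

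On either reading of 6.6, the placebo column holds no positive or negative counts.

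**Baseline.**
- The AXER-204 arm has an assayed Day 1 pre-dose sample and seven later ones (Days 21, 42, 63, 84, 104, 169, 253).
- SAP 8.7 lists all ADA data and summarises by time point, so Day 1 positives are visible as a count.
- No rule links a later result to the same subject's Day 1 result, and there is no treatment-induced or treatment-boosted category.
- SAP 8.8.3 makes this link for laboratory values: a new-onset abnormality requires none before treatment, and subjects abnormal at baseline leave the denominator. ADA has no equivalent rule.

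**What the by-visit counts cannot show (illustrative counts, not from the documents).** Take 16 AXER-204 subjects, with 2 positive at Day 1 and 4 positive at Day 104. The table shows 2/16 = 12.5% and 4/16 = 25%. Between 0 and 2 of the 4 may be the Day 1 positives, so new positives number 2 to 4 among the 14 who were negative at Day 1: 2/14 = 14.3% to 4/14 = 28.6%. Only the subject listing would settle which.

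**Possible size of carry-over (assumed inputs).** Let k of the 16 AXER-204 subjects have been in Part 1, and let a fraction f of them still be positive without having been re-induced. The visit percentage rises by k × f / 16:
- k = 2, f = 0.25: 0.5/16 = 3.1 points
- k = 4, f = 1: 4/16 = 25 points
- k = 8, f = 1: 8/16 = 50 points

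If f = 0 the addition is zero. The documents give neither k nor f.

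**Precision of one arm.** Exact 95% limits are 0% to 20.6% for 0/16 and 7.3% to 52.4% for 4/16. With counts this small, one or two misclassified subjects matter.

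**The case against.** The case for leaving the plan alone has force on several points.

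Not assaying placebo is a choice that the protocol states twice. Immunogenicity is not a Part 2 objective, and nothing promises a between-arm ADA comparison. The clinical immune and allergic events are adverse events collected in both arms and tabulated by treatment group (SAP 8.8.2), so that signal keeps its concurrent control. This stands, and it is why placebo testing is optional below.

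Some stronger readings are tempting, and the documents do not support them:
- *There is no usable baseline.* There is one. Day 1 is assayed in the AXER-204 arm and reported. The gap is that the incidence definition does not use it.
- *Part 1 antibodies will inflate Part 2 positivity.* The documents report no ADA-positive Part 1 subject and no persistence beyond 6 months. The 24 subjects in Part 1 are an enrolment ceiling, not a number expected to return. The effect is possible but not shown.
- *False positives will build up over seven samples.* No assay error rate is given, and SAP 8.7 plans counts by visit, not an ever-positive summary. At an assumed 1% to 5% per sample, a visit would hold 16 × 0.01 = 0.16 to 16 × 0.05 = 0.8 false positives.
- *Skipping placebo assays forces the laboratory to hold the codes.* Protocol 10.4.2 says "The bioanalytical laboratory personnel will be open to the randomization codes in order to facilitate PK analytical work and ADA testing", so the codes are opened for PK work as well, and the same section bars staff from passing the information on.
- *Placebo ADA is the check on treatment received.* Drug concentration would be the direct check, and the protocol also requires dispensing and accountability records.

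What the objection does not answer is the missing link to Day 1, or the SAP table that contradicts the protocol.

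**Conclusion.** Two limited faults stand. First, SAP 8.7 cannot separate antibodies induced by Part 2 dosing from those already present on Day 1, although the sample and the stratum needed to do so are in the design. Second, the by-treatment-group wording in SAP 8.7 and the unrestricted set in SAP 6.6 conflict with Protocol 13.2 and the synopsis, so a comparison is implied that cannot be made. A related gap is that Part 1 subjects randomised to placebo have no Part 2 ADA result, so persistence without re-dosing goes unmeasured.

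The size of the first fault depends on how many AXER-204 subjects are positive at Day 1, which the documents do not give. Each one still positive later, and not otherwise induced, adds 6.25 points at a visit on an arm of 16. If nobody is positive at Day 1, the numbers do not change. The second fault is certain, but it concerns reporting. The changes are worth making because they cost almost nothing. Sample size, alpha and the efficacy analyses are untouched.

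**What to change.** 1. In SAP 8.7, define treatment-emergent ADA in Part 2 as negative at Part 2 Day 1 and positive at a later visit. Add a boosted category, with a stated rise, if titres are available. Show Day 1 positives separately, and use Day 1 negatives as the denominator for induced ADA, as SAP 8.8.3 does for laboratory values.
2. Report these results by prior receipt of AXER-204 in Part 1 (yes/no).
3. Restrict the Part 2 ADA set (SAP 6.6) and table (SAP 8.7) to AXER-204 subjects, and state that there is no placebo comparison. This brings the SAP into line with Protocol 13.2 and the synopsis.
4. SAP section 10 shows that Day 169 results were unblinded to sponsor staff and the analysis team. Enter the change there and label it as made after unblinding.
5. Optional: assay the stored placebo serum for ADA, about 16 × 8 = 128 samples, and amend Protocol 13.2 and the synopsis to match. The two-arm table could then stay, and persistence in Part 1 subjects on placebo could be seen.

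Items 1 to 4 cost SAP text and table programming. Item 5 costs assays on serum already collected. None needs a new sample or visit.
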